Management of Select Laboratory Abnormalities: For any given laboratory abnormality, the Investigator should assess the subject, apply the standard of care for medical evaluation and treatment following any local guidelines. Specific toxicity management guidelines for abnormal laboratory values are described in Table 4 and may require an appropriate supplemental eCRF be completed. For subjects with ongoing laboratory abnormalities which require data entry into an eCRF, an additional eCRF related to subsequent laboratory abnormalities is only required if the subject has relevant changes in history (e.g., new onset signs or symptoms) or laboratory values which have returned to normal reference range or its Baseline value followed by subsequent laboratory abnormalities meeting toxicity guidelines (considered a new event). All abnormal laboratory tests that are considered clinically significant by the Investigator will be followed to a satisfactory resolution. If a repeat test is required per Table 4, the repeat testing must occur as soon as possible.

[figure not shown]
[figure not shown]

Table 4. Specific Toxicity Management Guidelines for Abnormal Laboratory Values

Laboratory Parameter	Toxicity Management Guideline
Hemoglobin	 If hemoglobin < 8 g/dL interrupt study drug dosing and confirm by repeat testing with a new sample. If hemoglobin decreases ≥ 3.0 g/dL from Baseline without an alternative etiology, interrupt study drug dosing and confirm by repeat testing with new sample. If hemoglobin decreases ≥ 3.0 g/dL from Baseline and an alternative etiology is known or the hemoglobin value remains in the normal reference range, the subject may remain on study drug at the investigator's discretion. If confirmed, continue to withhold study drug until hemoglobin value returns to normal reference range or its Baseline value.
Absolute neutrophil count (ANC)	 If confirmed < 1000/μL by repeat testing with new sample, interrupt study drug dosing until ANC value returns to normal reference range or its Baseline value. Interrupt study drug if confirmed < 500/μL by repeat testing with new sample. If value returns to normal reference range or its Baseline value, restarting study drug is allowed if there is an alternative etiology identified; documentation should include reason that rechallenge is expected to be safe for the subject. Study drug should be discontinued if no alternative etiology can be found.

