	Subjects who meet any of the above criteria should be evaluated for an alternative etiology of the ALT or AST elevation and managed as medically appropriate. If applicable, the alternative etiology should be documented appropriately in the eCRF. If ALT or AST values return to the normal reference range or its Baseline value, study drug may be restarted. If restarting study drug, documentation should include reason that rechallenge is expected to be safe. If after clinically appropriate evaluation, no alternative etiology for ALT or AST elevation is found or the ALT or AST elevation has not resolved or is not trending down toward normal, the subject should be discontinued from study drug. For any confirmed ALT or AST elevation > 3 ULN, complete the appropriate supplemental hepatic eCRF(s).
Serum Creatinine	• If serum creatinine is > 1.5 × the Baseline value and > ULN, repeat the test for serum creatinine (with subject in an euvolemic state) to confirm the results. If the results of the repeat testing still meet this criterion then interrupt study drug and re-start study drug once serum creatinine returns to ≤ 1.5 × Baseline value.
	• If confirmed serum creatinine ≥ 2 mg/dL, interrupt study drug and re-start study drug once serum creatinine returns to normal reference range or its Baseline value.

Laboratory Parameter	Toxicity Management Guideline
	For the above serum creatinine elevation scenarios, complete the appropriate supplemental renal eCRF(s).
Creatine Phosphokinase	• If confirmed CPK value ≥ 4 × ULN and there are no symptoms suggestive of myositis or rhabdomyolysis, the subjects may continue study drug at the investigator's discretion.
	 If confirmed CPK ≥ 4 × ULN accompanied by symptoms suggestive of myositis or rhabdomyolysis, interrupt study drug and contact AbbVie TA MD.
	For the above CPK elevation scenarios, complete supplemental CPK eCRF.

For study drug interruption, the following rules apply:

- For upadacitinib/placebo (daily dosing):
 - Ouring first 24 weeks, study drug interruption of \leq 14 consecutive days is allowed.
 - After Week 24, study drug interruption of \leq 21 consecutive days is allowed.
- For adalimumab/placebo (biweekly dosing):
 - Ouring first 24 weeks, study drug interruption is allowed \leq 2 consecutive missed doses.
 - After Week 24, study drug interruption is allowed ≤ 3 consecutive missed doses.
- If the subject must undergo emergency surgery, the study drugs should be interrupted at the time of the surgery.

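### Table 4's ALT/AST row both permits restart and directs discontinuation for a subject whose enzymes normalise and whose work-up finds no other cause

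*Protocol*

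**What the plan says.** All of the relevant text is in Protocol Section 6.1.7, Table 4.

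The ALT/AST row, after listing its interruption criteria, has four parts:

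- **Work-up.** "Subjects who meet any of the above criteria should be evaluated for an alternative etiology of the ALT or AST elevation".
- **Restart.** "If ALT or AST values return to the normal reference range or its Baseline value, study drug may be restarted".
- **Documentation.** "If restarting study drug, documentation should include reason that rechallenge is expected to be safe".
- **Discontinuation.** Once appropriate evaluation is done, the first two triggers are "no alternative etiology for ALT or AST elevation is found or the ALT or AST elevation has not resolved". A third, again joined by or, covers enzymes that are failing to fall. For any one of them the instruction is "the subject should be discontinued from study drug".

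The neutrophil row of the same table, in its rule for confirmed counts below 500/µL, is built differently. After recovery, "restarting study drug is allowed if there is an alternative etiology identified". Its counterpart reads "Study drug should be discontinued if no alternative etiology can be found".

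**The concern.** The restart sentence looks only at the enzyme values. The discontinuation sentence looks at the enzyme values and at the result of the work-up, and either can trigger it. Because the work-up is required for everyone who meets a criterion in the row, a negative result in someone whose enzymes have recovered is a foreseeable outcome.

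Two sites reading the same row could then act differently on the same kind of subject, one re-exposing and the other stopping for good.

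The choice also reaches the data. Protocol Section 5.3.1.1 (Clinical Laboratory Tests) makes a laboratory value that requires stopping study drug an adverse event. Which sentence a site follows can therefore affect whether an event is recorded and whether it counts as a discontinuation due to an adverse event in the long-term safety summaries (Protocol Section 8.1.5.2.1; SAP Section 10.2.2.1).

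**Working it through.** No figure in the plan is at issue, so the check is logical: write each sentence as a condition and look for states that satisfy both.

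**Definitions**

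- Enzyme state: normalised (back to the normal range or Baseline), falling but not normalised, or not falling.
- Work-up: another cause found, or not found.
- Restart permitted if: normalised.
- Discontinue if: no cause found, or not resolved, or not falling.

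The row does not define resolved. I take it to mean the same as the recovery named in the restart sentence. I also take the not-falling limb not to apply to a value already back to normal.

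**Enumeration: 3 × 2 = 6 states**

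| State | Enzymes | Other cause | Restart sentence | Discontinuation sentence |
|---|---|---|---|---|
| 1 | Normalised | Found | Applies | Does not apply |
| 2 | Normalised | Not found | **Applies** | **Applies** |
| 3 | Falling | Found | Does not apply | Applies (not resolved) |
| 4 | Falling | Not found | Does not apply | Applies |
| 5 | Not falling | Found | Does not apply | Applies |
| 6 | Not falling | Not found | Does not apply | Applies |

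One state of six, state 2, falls under both sentences.

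**Does the drafting of the discontinuation sentence matter?** Two readings both remove the overlap, and they give opposite answers in state 2:

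- If restart is silently conditional on an identified cause, as in the neutrophil rule, state 2 becomes discontinue only.
- If the first or was meant as and, discontinuation needs no cause found together with failure to recover. State 2 then becomes restart only, and states 3 and 5 are left with neither sentence.

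The text states neither reading.

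**Secondary drafting point.** A value that is not falling toward normal is also not resolved. Joined by or, the not-falling limb therefore adds no state that the not-resolved limb has not already caught (states 3 to 6). It does work only if those two limbs are joined by and, in which case state 3 drops out of the discontinuation sentence. That change would leave state 2 untouched.

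**Side by side with the neutrophil rule.** There, restart requires a cause to be identified and discontinuation applies when none is found. The two conditions are complements, so no recovered subject can meet both.

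**Is the ranking supplied elsewhere in the protocol?**

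- Section 5.4.1 leaves discontinuation for significant laboratory results to the investigator or the sponsor's medical director. It does not rank the two sentences.
- Section 5.5.4 and the interruption rules after Table 4 limit an oral-drug interruption to 14 consecutive days in the first 24 weeks and 21 afterwards. They are silent on cause, so the overlap remains for anyone who recovers within the limit.
- Within the row, contact with the medical director is required only for a confirmed value above 8 × ULN.
- The opening of Section 6.1.7 removes subjects who are off study drug and on standard of care from these rules. That narrows who is affected but does not resolve the conflict for those on drug.

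**The case against.** The strongest reply is that the sentences are not two commands. Restart is a permission and discontinuation a directive, so a site that stops drug complies with both and a site that restarts departs from the directive. The row also runs in order (evaluate, allow restart with a recorded reason, then limit), and the neutrophil rule has the same ingredients. On this view the later sentence governs.

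Part of this stands. The defect is an unstated priority between a permission and a directive. But the row contains no wording that makes one sentence subject to the other, and the analogy does not settle it. The lymphocyte, white-cell and platelet rows of the same table let recovery alone end an interruption, so there is no uniform condition on cause to import.

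Four stronger readings are tempting and not supported:

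- A reader might infer that a falling value with a cause found is also contradictory. It is not. The restart sentence requires full recovery, so only discontinuation applies. Nor is waiting ruled out, because that sentence takes effect only after evaluation.
- A reader might infer that the discontinuation sentence contradicts itself. A redundant limb is loose drafting, not a contradiction.
- A reader might infer that recovery off drug with no cause found marks drug injury, and so settles the clinical answer. Table 4 does not say this, and the choice is not one for a statistical review.
- A reader might infer damage to the main efficacy results through non-responder imputation. SAP Section 11.1 records the primary efficacy and Period 1 reporting as complete. Long-term efficacy rests mainly on As Observed data, with non-responder imputation and/or a mixed model as an addition (SAP Section 9.3).

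**Conclusion.** The point holds for one state: enzymes back to normal or Baseline, with no other cause found. There the ALT/AST row permits restart and directs discontinuation, and nothing in the protocol says which prevails. The redundant not-falling limb is a minor drafting fault in the same sentence.

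The conclusion rests on reading or literally and on equating resolved with the recovery in the restart sentence. It concerns subjects still on study drug who recover within the permitted interruption.

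The consequence is possible inconsistent handling between sites, with a possible effect on long-term counts of discontinuations due to adverse events. Neither document gives a rate for this state, so the size cannot be computed. The completed Week 24 and Period 1 analyses are not affected. Because this is a stop-or-restart safety rule, it merits correction even without a measurable statistical effect.

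**What to change.** Reconcile the restart and discontinuation sentences in the ALT/AST row so that each combination of enzyme state (normalised, falling, not falling) and work-up result (cause found, not found) leads to exactly one instruction. The revised text should state:

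- whether restart is conditional on an identified cause;
- whether each or in the discontinuation sentence is intended, including the one that makes the not-falling limb redundant.

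Which outcome applies in each state is for the sponsor's medical team to decide. The neutrophil rule is a model for non-overlapping structure only, not for the clinical answer.

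The cost is rewording one table row, in the next amendment or a clarification letter to sites, with matching wording in the supplemental hepatic eCRF. No visits, tests or analyses are added.

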- 9. Receipt of any live vaccine within 4 weeks (8 weeks in Japan) prior to the Baseline Visit, or expected need of live vaccination during study participation including at least 4 weeks (8 weeks in Japan) after the last dose of oral study drug, and including at least 70 days after the last dose of subcutaneous study drug.
- 10. Subject has received oral or parenteral Traditional Chinese Medicines within 4 weeks prior to Baseline, has received opioid analgesics (except for tramadol or combination of acetaminophen and codeine or hydrocodone which are allowed)

- within 1 week prior to Baseline, or use of inhaled marijuana within 2 weeks prior to Baseline.
- 11. History of an allergic reaction or significant sensitivity to constituents of the study drugs (including adalimumab or its excipients) and/or other products in the same class.
- 12. History of fibromyalgia, any arthritis with onset prior to age 17 years or current diagnosis of inflammatory joint disease other than PsA (including, but not limited to rheumatoid arthritis, gout, overlap connective tissue diseases, scleroderma, polymyositis, dermatomyositis, systemic lupus erythematosus.) Prior history of reactive arthritis or axial spondyloarthritis including ankylosing spondylitis and non-radiographic axial spondyloarthritis is permitted if documentation of change in diagnosis to PsA or additional diagnosis of PsA is made. Prior history of fibromyalgia is permitted if documentation of change in diagnosis to PsA or documentation that the diagnosis of fibromyalgia was made incorrectly.
- 13. History of clinically significant (per Investigator's judgment) drug or alcohol abuse within the last 6 months preceding the Baseline Visit.
- 14. Female subject who is pregnant, breastfeeding or is considering becoming pregnant during the study within 150 days after the last dose of subcutaneous study drug, and within 30 days after the last dose of oral study drug.
- 15. Laboratory values meeting the following criteria within the Screening period:
 - Serum aspartate transaminase (AST) $> 2 \times ULN$;
 - Serum alanine transaminase (ALT) $> 2 \times ULN$;
 - Estimated glomerular filtration rate (GFR) by simplified 4-variable Modification of Diet in Renal Disease (MDRD) formula
 40 mL/min/1.73 m²;
 - Total white blood cell count (WBC) < 2,500/μL;
 - Absolute neutrophil count (ANC) $< 1,500/\mu L;$
 - Platelet count $< 100,000/\mu L$;
 - Absolute lymphocyte count < 800/μL;

- Hemoglobin < 10 g/dL.

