For clinic visits where samples for serum chemistry tests are collected, subjects should be fasting (a minimum 8-hour fast) whenever possible. If a subject is not able to fast when necessary, due to unforeseen circumstances, the non-fasting status will be recorded in study source documentation.

Urine samples will be obtained for urinalysis testing at the specified time points as noted in Appendix C. The central laboratory will be responsible for performing a macroscopic

urinalysis (urine dipstick) on the collected urine specimens. Specified abnormal macroscopic urinalyses defined as leukocytes, nitrite, protein, ketones or blood greater than negative, or glucose greater than normal will be followed-up with a microscopic analysis at the central laboratory.

For any laboratory test value outside the reference range that the Investigator considers to be clinically significant, the Investigator should apply the standard of care for medical evaluation and treatment per local guidelines:

- The Investigator will repeat the test to verify the out-of-range value.
- The Investigator will follow the out-of-range value to a satisfactory clinical resolution.

A laboratory test value that requires a subject to be discontinued from study drug treatment or requires a subject to receive treatment will be recorded as an AE. The central laboratory chosen for this study will provide instructions regarding the collection, processing and shipping of these samples. The baseline laboratory test results for clinical assessment for a particular test will be defined as the last measurement prior to the initial dose of study drug.

[figure not shown]
[figure not shown]

Table 2. Clinical Laboratory Tests

Hematology	Clinical Chemistry ^a	Urinalysis ^b	Other Laboratory Tests
(Central Lab)	(Central Lab)	(Central Lab)	

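### Table 4 gives two serum creatinine rules with different restart points and no precedence; above a Baseline of about 1.33 mg/dL one can order restart at a value where the other orders interruption

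*Protocol*

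**What the plan says.** The serum creatinine row of Table 4 (Protocol Section 6.1.7) holds two bullets.

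- Bullet 1: "If serum creatinine is > 1.5 × the Baseline value and > ULN, repeat the test for serum creatinine"; if the repeat still meets the criterion, "then interrupt study drug and re-start study drug once serum creatinine returns to ≤ 1.5 × Baseline value".
- Bullet 2: "If confirmed serum creatinine ≥ 2 mg/dL, interrupt study drug". Its own restart condition is worded differently: "re-start study drug once serum creatinine returns to normal reference range or its Baseline value".

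The only text joining them is an instruction to complete the renal eCRF for either scenario. No sentence says which restart condition applies when both triggers have been met.

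Three other provisions bear on the point.

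- Protocol Section 5.3.1.1 takes the baseline laboratory value as the one "defined as the last measurement prior to the initial dose of study drug".
- Exclusion criterion 15 (Section 5.2.2) limits renal function by "Estimated glomerular filtration rate (GFR) by simplified 4-variable Modification of Diet in Renal Disease (MDRD) formula", with a limit of 40 mL/min/1.73 m². It sets no limit on creatinine itself.
- Section 5.5.4 requires study drug to be discontinued after an oral interruption of more than 21 consecutive days once past Week 24 (14 days before that).

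**The concern.** The bullets look like alternatives, but one creatinine course can trigger both. A site must then choose a restart value, and two sites with the same results could choose differently. At a higher Baseline the conflict is direct: a value low enough to restart under one bullet is high enough to interrupt under the other.

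At stake is when a subject with a confirmed creatinine rise goes back on drug. The longer hold also uses up the interruption allowance, so the choice of bullet can decide between continuing and being withdrawn. Recording is touched too. Section 6.1.7 calls for a further eCRF only after a relevant change in history, or after the value has returned to the normal range or Baseline and then risen again. A subject with Baseline 1.0 and an assumed ULN of 1.2 mg/dL who restarts at 1.4 under bullet 1 has not made that return.

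**Working it through.** The documents state no derived figure here, so there is nothing to reproduce. I evaluated the two rules as written.

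**Notation.** b = Baseline, c = current confirmed creatinine, u = ULN, all in mg/dL.

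- Bullet 1 interrupts if c > 1.5b and c > u, and restarts at c ≤ 1.5b.
- Bullet 2 interrupts if c ≥ 2, and restarts at c ≤ u or c ≤ b, that is, at or below the larger of the two.

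**Assumption.** The documents give no ULN for creatinine. I used 0.9 to 1.3 mg/dL.

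**Step 1: when both are met at 2 mg/dL.** This needs 2 > 1.5b, so b < 2/1.5 = 1.33, and u < 2.

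**Step 2: restart points** (mg/dL)

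| Baseline | Bullet 1: 1.5b | Bullet 2, ULN 0.9 | Bullet 2, ULN 1.1 | Bullet 2, ULN 1.3 |
|---|---|---|---|---|
| 0.6 | 0.90 | 0.9 | 1.1 | 1.3 |
| 0.8 | 1.20 | 0.9 | 1.1 | 1.3 |
| 1.0 | 1.50 | 1.0 | 1.1 | 1.3 |
| 1.3 | 1.95 | 1.3 | 1.3 | 1.3 |
| 1.5 | 2.25 | 1.5 | 1.5 | 1.5 |

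At Baseline 1.0 bullet 1 is the looser rule by 0.2 to 0.5 mg/dL. At Baseline 0.6 it is the stricter one by 0 to 0.4. The two points coincide where 1.5b = u: at b = 0.6 for ULN 0.9, and at b = 0.8 for ULN 1.2.

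**Step 3: restart against interruption.** A value that satisfies bullet 1's restart and bullet 2's interruption needs 2 ≤ c ≤ 1.5b. Such a range exists once b is above about 1.33. Any subject there who triggers bullet 1 has c > 1.5b > 2 and so has triggered bullet 2 as well. Example: b = 1.5 and peak 2.4. The peak exceeds 1.5 × 1.5 = 2.25, so both bullets apply. On the way down, from 2.25 to 2.00, bullet 1 says restart and bullet 2 says interrupt. A peak between 2 and 2.25 would trigger bullet 2 only, and no conflict would arise.

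**Step 4: can such a subject be enrolled?** The protocol does not print the MDRD constants, so I assumed the standard form with a constant of 175 or 186. For a man of 50 at 1.5 mg/dL, 175 × 1.5^-1.154 × 50^-0.203 is about 50, above the limit of 40. The creatinine corresponding to eGFR 40 is about 1.7 to 2.1 mg/dL for men aged 30 to 75 and about 1.3 to 1.6 for women. The range is therefore open to men throughout these ages. For women it depends on age and constant: with 175, a woman of 65 at 1.334 mg/dL has eGFR 39.9.

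**Step 5: how many subjects?** The documents give neither a Baseline creatinine distribution nor an expected number reaching 2 mg/dL. In simulations with an assumed Baseline mean of 0.80 to 0.90 (SD 0.18 to 0.25), about 1% to 5% of subjects had Baseline at or above 1.333. With an assumed SD of 0.15 to 0.40 for the log fold-rise, the share of those reaching 2 mg/dL who met both bullets ran from 19% to 98%. That spread reflects the assumptions and is not an estimate for this trial.

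**The case against.** The strongest reply is that the holds are cumulative: each bullet imposes its own hold and says when that hold ends, so a subject under both must clear both. Nobody would then restart at 2.00 to 2.25 mg/dL. The ANC row also has two overlapping levels without a precedence sentence.

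That reading is reasonable, but it is not written. It leaves bullet 1's restart order without effect at high Baseline, and at low Baseline it lets bullet 1 block a restart that bullet 2 orders (Baseline 0.6, ULN 1.1, value 1.0). The ANC levels differ from this: both use the same recovery value, and the lower level adds a condition.

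The objection succeeds on consequences. The Amendment 8 summary of changes (Protocol Section 1.1) lists the creatinine restart criteria among its updates, and the synopsis is dated 20 December 2023. SAP Appendix F puts the Week 24 lock in January 2020, and SAP Section 11.1 reports that the primary efficacy analysis and Period 1 reporting are complete. A reader might infer that differing restarts could feed non-responder imputation for the primary or ranked endpoints. This text comes too late for that, and the 14-day limit is largely moot for the same reason. Long-term efficacy is summarised mainly as observed (SAP Section 9.1.1), with imputation as one unranked option (SAP Section 9.3). Nor does the restart point decide whether renal dysfunction is captured as an event of special interest, because SAP Table 11 identifies it by a MedDRA query.

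**Conclusion.** The conflict is real and should be fixed. Two bullets can bind the same subject, they generally set different restart points, and no precedence is stated. For an eligible Baseline above about 1.33 mg/dL, bullet 1 can order restart at a value of 2 mg/dL or more, where bullet 2 orders interruption. The 1.33 cut-off is arithmetic on the protocol's own figures. The overlap below it assumes ULN under 2 mg/dL, the size of the gaps rests on the assumed ULN, and the eligibility of high-Baseline subjects rests on the assumed MDRD constants.

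Two stronger readings are not supported. A reader might infer that nearly everyone reaching 2 mg/dL meets both bullets, but that needs a Baseline distribution the documents do not give. A reader might also infer that the restart points differ at every Baseline below 1.33, but they coincide where 1.5 × Baseline equals ULN, and below that the direction reverses.

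The practical effect is on safety handling and the 21-day interruption limit in late Period 2. How many subjects would be managed differently, or withdrawn, cannot be derived.

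**What to change.** Reconcile the two creatinine bullets in Table 4. State which restart condition governs a subject who has met both triggers, and remove the range in which one bullet orders restart at a value that triggers the other. The wording should be checked at a low Baseline (0.6 mg/dL) as well as a high one (1.5 mg/dL), because the two bullets change order between them. The medical team decides the threshold; no view is taken here on which is right.

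The cost is rewording one table row, by amendment or clarification letter. It adds no tests or visits.
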